12.3.2 Vital signs

Vital signs will be measured at time points specified in Section 1.8 and comprise pulse rate, systolic and diastolic blood pressure, and respiratory rate.

Vital signs will be measured in a sitting position after resting for 10 minutes. While resting, the subject should not receive anything to drink or eat.

12.3.3 Safety laboratory

Sampling for clinical laboratory parameter assessment and for urinalysis will be done at the Enrollment Visit (see schedule of events in Section 1.8). The blood samples will be taken by direct venipuncture or by means of an indwelling venous cannula.

Clinical laboratory parameter assessment will be performed by contracted local certified clinical laboratories. Details on the clinical laboratories will be held in the trial master file and the investigator's site file.

A table of the reference ranges for each of the clinical laboratory parameters measured with a description of the methods will be provided by the clinical laboratory before the trial start and will be filed in the investigator's site file and the trial master file. Changes in the reference ranges or in the methodology during the course of the trial must be communicated by the local clinical laboratory to the investigators and to the sponsor.

Throughout the clinical part of the trial, the investigator must provide feedback regarding the clinical relevance of any laboratory value outside the reference range.

Additional determination of several parameters from blood may be added at the discretion of the investigator.

If clinical laboratory parameters exceed the pre-defined alert ranges (i.e., 1 standard deviation above or below the upper/lower limit of the normal range) the subject must not be allocated to treatment.

The original printouts of the clinical laboratory parameter and (if applicable) urinalysis values will be considered source documents and will be stored in the subject files. Data will be transferred from the printouts to the CRF by the investigator.

For each subject, up to 3 blood samples (total volume 12 mL) will be drawn for clinical laboratory parameter assessments.

The following clinical laboratory parameters will be assessed:

Clinical chemistry panel (sample volume approximately 6 mL)

Sodium	Total bilirubin
Potassium	Alkaline phosphatase
Chloride	Creatine kinase
Bicarbonate	Lactate dehydrogenase
Urea	Uric acid
Creatinine (serum)	Calcium

Clinical chemistry panel (sample volume approximately 6 mL)

Glucose	Phosphorus
Aspartate transaminase	Albumin
Alanine transaminase	Total protein
Gamma-glutamyl transferase	Lipase
Cholesterol	Triglycerides

Hematology panel (sample volume approximately 3 mL)

Hemoglobin	Platelet count
Hematocrit	White blood cell count; manual differential white blood cell count if automatic differential white blood cell count is abnormal
Red blood cell count	Mean cell volume
Mean cell hemoglobin	Mean cell hemoglobin concentration

Coagulation panel (sample volume approximately 3 mL)

Activated partial thromboplastin time	International normalized ratio (derived from the prothrombin time)
Prothrombin time	

Urinalysis panel

pH	Protein
Glucose	Ketones
Urobilinogen	Bilirubin
Hemoglobin	Nitrite
Leukocytes	

If urinalysis results are positive for leukocyte esterase, nitrite, protein, or blood, a microscopic examination of urine must be performed. Results will be reported only for the parameters that are present.

12.4 Appropriateness of measurements

The selection of the outcome measures pain intensity and pain relief and the derived parameters SPID and TOTPAR to support the secondary endpoints are commonly used in single-dose acute pain trials (Cooper et al. 2016). The visual analog scale is amongst the most popular scales to measure acute pain. The assessment of the onset of the analgesic effect using the double-stopwatch method is standardized and reliable (Desjardins et al. 2002).

The TOTPAR was selected because this summary measure is widely used and acknowledged for the scientific evaluation of single-dose trials (Sriwatanakul et al. 1983) and is an accepted endpoint for acute pain trials (Singla et al. 2015). The TOTPAR scores can be interpreted as estimates of the area under the longitudinal pain relief curve. The time-frame of 4 hours has been chosen as it coincides with the time point the comparator concentrations drop below published minimum effective concentrations, and as it minimizes the impact of potential rescue medication intake.

12.5 Compliance

Compliance is the adherence to all requirements of the trial protocol.

Trial site compliance will be assured by the implementation of a quality system and the performance of a combination of trial site visits, training, and monitoring visits. Non-compliance should lead to prompt action by the sponsor to secure compliance.

Subject compliance will be confirmed by a comparison of IMPs dispensed and returned and by IMP administration by the investigator in a controlled environment.

13 DOCUMENTATION OF TRIAL DATA

The trial documentation must be adequate for the reconstruction of the trial.

13.1 Case report forms

The investigator must verify and confirm by signing that the CRFs have been checked and are complete, accurate, and compatible with the source documents. All CRF entries, corrections, and alterations must be made by the investigator or other authorized personnel under their supervision.

Case report forms for each subject will be provided to the investigator by the sponsor in electronic format to document the trial data.

The investigator and personnel delegated the task will use CRFs to record information required by the protocol. All personnel entering data will receive instruction on how to complete the CRF.

The investigator will be required to verify that the CRF entries are complete, accurate, and compatible with source documents.

All CRF entries, corrections, and alterations will be made by the investigator or other authorized personnel under their supervision. Entries will be checked against appropriate source documents by authorized sponsor representatives as deemed appropriate in the monitoring guidelines.

The data will be processed using a validated electronic CRF system. Access to the system will be protected with a personal user name and password. Dedicated users (e.g., the investigator, designated persons at the trial site, authorized sponsor representatives, and from other parties involved, e.g., data management) will be identified and receive access rights according to their role in the trial. They will be trained on the use of the system for their intended role before access rights are granted and will be able to review data during the trial via a secure internet connection.

All entries and modifications to the CRF will be stored with the personal identification of the person who made the entry/changes, a date/time stamp, and the reason for change, if applicable.

The CRF must be signed electronically by the investigator. Any changes made to the CRF pages after the investigator has signed will require re-signing by the investigator.

13.2 Subject reported outcomes

Subject's pain assessments (NRS), pain relief scores, responses to the question if pain is at least half gone, and IMP/rescue medication intake at home will be captured by paper.

All subject reported outcomes reported on paper will stay as source data at the trial site. The investigator is responsible for the accurate transfer of these data into the CRFs (see Section 13.1).

13.3 Data management

Data management will be performed by sponsor personnel or by authorized sponsor representatives. Documentation of the responsibilities and delegation thereof will be maintained in the trial master file.

Queries and corrections

During data entry in the CRF, automatic queries will be raised to clarify missing data, inconsistencies, and incorrect values. Additional queries will be issued via the CRF system to the investigator to clarify inconsistencies (e.g., resulting from additional electronic validation checks or medical and manual reviews). Resolutions of queries will be made by the investigator or the trial site's designated persons. The query is to be answered directly in the electronic CRF system and the original value will be changed, if necessary.

Corrections to the data without raising a query to the investigator will only be made by the data management CRO when the errors and their solutions are self-evident and if they do not change the actual meaning of the data as recorded by the investigator.

A list of all self-evident corrections will be defined in the data management plan and will be sent to the investigator for approval at the beginning of the trial. If the investigator does not approve the list of self-evident corrections, data clarification forms will be created.

External trial data

External trial data (e.g., clinical laboratory parameters) being provided on separate printouts will be entered manually directly from the printouts.

The transferred data will be reconciled against other CRF data (details of reconciliation will be specified separately in the data validation plan or data management plan but may include trial code, trial site number, subject number, age, dates of visits). Procedures will be implemented to resolve discrepancies.

At the end of the trial, the providers/vendors providing these data will provide the data management CRO with a complete and clean data transfer.

Coding

Medication names will be coded using the World Health Organization-Drug Dictionary (WHO-DD). Medical history terms and adverse events will be coded using the Medical Dictionary for Regulatory Activities (MedDRA). Coding will be reviewed by the sponsor's personnel according to standard procedures.

Database lock

When all data have been received and entered into the clinical trial database, all data checks and quality control checks have been performed, all queries are resolved, and the final statistical review has been held without resulting in new queries, the clinical trial database will be considered clean and the data will be locked.

13.4 Source data

Source data is defined by GCP as “all information in original records and certified copies of original records of clinical findings, observations, or other activities in a clinical trial necessary for the reconstruction and evaluation of the trial. Source data are contained in source documents (original records or certified copies)”.

Source data comprise clinical documentation, data, and records (e.g., clinic/hospital records, clinical and office charts, laboratory notes, memoranda, subjects’ diaries or evaluation checklists, pharmacy dispensing records, recorded data from automated instruments, and data and records arising from departments such as the pharmacy, laboratory, and medico-technical departments) that describe or record the methods, conduct, or results of the trial, the factors affecting the trial, and the actions taken.

All source data arising from the trial will be kept by the investigator, who must provide direct access for trial-related monitoring, audits, ethics committee review, and regulatory inspection.

In certain circumstances, data may only be recorded in the trial-specific CRF and not in other documents. When this occurs, the CRF is considered to be the source document. Data expected to be only recorded in the CRF are: race/ethnicity and sex.

The nature and location of all source data/clinical documentation will be identified and documented by the investigator to ensure that all sources of original data required to complete the CRF are known to the sponsor and/or trial site personnel and are accessible for verification during trial-related monitoring, audits, relevant IEC review, and inspection(s).

During trial conduct, the vendor is responsible for data security related to data captured in the electronic CRF or IRT.

All data captured from all subjects will be sent to the sponsor in human readable form on a read-only compact disc/DVD for filing/archiving according to sponsor SOPs.

The investigator will receive all data captured for his or her subjects, in a human readable form, on a read-only compact disc/DVD for his or her files.

13.5 Investigator’s site file and the trial master file

The principal investigator is responsible for the filing of all essential documents in an investigator’s site file. The sponsor is responsible for the timely filing of all essential documents in the trial master file. As applicable, these files must be available at monitoring visits and during audits or regulatory inspections.

After trial completion, the principal investigator must ensure that all source data/documentation related to the trial is recorded, handled, and stored in a way that allows its accurate reporting, interpretation and verification. The principal investigator must take measures to prevent accidental or premature destruction of these documents.

The principal investigator must keep the investigator’s site file, the source data/documentation arising from the trial according to the prescribed record retention period in the country and/or according to the hospital policy, but at least until informed by the sponsor that the trial-related records are no longer required.

14 QUANTITATIVE ANALYSES

14.1 Statistical methods and sample size determination

14.1.1 Sample size rationale

A total number of 720 subjects or 180 subjects per treatment group are required to achieve an overall power of at least 85% to reject the null hypothesis of at least 1 of the 4 formal statistical tests in the primary analysis of the trial (1-sided t-test, type I error of $\alpha/4$ with $\alpha = 2.5\%$) assuming a common standard deviation of change from baseline values of 4 points (TOTPAR4) (Bakshi et al. 1994, Hersh et al. 2004) and an expected treatment difference of at least 2 points (TOTPAR4) (Aquad et al. 2009, Singla et al. 2014) on the primary efficacy endpoint in the comparisons between tramadol HCl/diclofenac sodium 50 mg/50 mg and the monotherapies of diclofenac sodium 50 mg and tramadol HCl 50 mg, and using a non-inferiority margin of $\Delta = 1.5$ points (TOTPAR4) (see Section 18.2) on the primary efficacy endpoint in the comparisons between tramadol HCl/diclofenac sodium 25 mg/25 mg and the monotherapies of diclofenac sodium 50 mg and tramadol HCl 50 mg. To achieve 180 evaluable subjects per arm and accounting that up to 10% of subjects will not be evaluable for the analysis set for the primary analysis, 200 subjects per arm or 800 subjects in total will be allocated to IMP.

Assuming an enrollment failure rate of about 25% which is usually observed in clinical trials in Mexico, about 1065 subjects are planned to be enrolled (i.e., sign the informed consent) in order to allocate 800 subjects to IMP, i.e., about 130 subjects per trial site in approximately 8 to 12 sites.

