14.5.2 Overall testing strategy

The primary objective of the trial (see Section 1.2) is investigated by 4 formal statistical tests (see Table 1). Testing multiple hypotheses, however, may increase the family-wise type I error rate, the probability to erroneously reject at least 1 true null hypothesis, beyond the pre-specified significance level. In order to control the family-wise type I error rate in the strong sense at the pre-specified 1-sided significance level of $\alpha = 2.5\%$, a Bonferroni-Holm procedure (Holm 1979) will be used. The elementary null hypotheses H_{01} , H_{02} , H_{03} , and H_{04} and according statistical tests T_1 , T_2 , T_3 , and T_4 of the primary objective of the trial are listed in Table 1.

Table 1: Statistical tests and null hypotheses (all 1-sided) of the primary objective of the trial

Test	Description	Null hypothesis	Alternative hypothesis
T_1	Superiority of tramadol HCl/diclofenac sodium 50 mg/50 mg vs. tramadol HCl 50 mg	$H_{01}: \mu_{T50} - \mu_{ADL50/50} \geq 0$	$H_{A1}: \mu_{T50} - \mu_{ADL50/50} < 0$
T_2	Superiority of tramadol HCl/diclofenac sodium 50 mg/50 mg vs. diclofenac sodium 50 mg	$H_{02}: \mu_{D50} - \mu_{ADL50/50} \geq 0$	$H_{A2}: \mu_{D50} - \mu_{ADL50/50} < 0$
T_3	Non-inferiority of tramadol HCl/diclofenac sodium 25 mg/25 mg vs. tramadol HCl 50 mg	$H_{03}: \mu_{T50} - \mu_{ADL25/25} \geq \Delta$	$H_{A3}: \mu_{T50} - \mu_{ADL25/25} < \Delta$
T_4	Non-inferiority of tramadol HCl/diclofenac sodium 25 mg/25 mg vs. diclofenac sodium 50 mg	$H_{04}: \mu_{D50} - \mu_{ADL25/25} \geq \Delta$	$H_{A4}: \mu_{D50} - \mu_{ADL25/25} < \Delta$

ADL = Adorlan (tramadol HCl/diclofenac sodium); D = diclofenac sodium; T = tramadol hydrochloride; HCl = hydrochloride.

$\Delta = 1.5$ is the non-inferiority margin.

The trial will be positive if at least 1 of the according 4 statistical tests rejects the according null hypothesis.

According the Bonferroni-Holm procedure, the p-values of the 4 tests T_1 , T_2 , T_3 , and T_4 will be sorted in ascending order $p_{(1)} < p_{(2)} < p_{(3)} < p_{(4)}$ and the following algorithm will be applied to the corresponding null hypotheses $H_{(01)}$, $H_{(02)}$, $H_{(03)}$, $H_{(04)}$:

- Step 1. If $p_{(1)} < \alpha/4 = 0.625\%$, reject $H_{(01)}$ and move to the next step. Otherwise retain all null hypotheses and stop.
- Step 2. If $p_{(2)} < \alpha/3 = 0.833\%$, reject $H_{(02)}$ and move to the next step. Otherwise retain $H_{(02)}$, $H_{(03)}$ and $H_{(04)}$ and stop.

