4. DETERMINATION OF SAMPLE SIZE

A total number of 720 subjects or 180 subjects per treatment group are required to achieve an overall power of at least 85% to reject the null hypothesis of at least 1 of the 4 formal statistical tests in the primary analysis of the trial (1-sided t-test, type I error of $\alpha/4$ with $\alpha = 2.5\%$) assuming a common standard deviation of change from baseline values of 4 points (TOTPAR4) and an expected treatment difference of at least 2 points (TOTPAR4) on the primary efficacy endpoint in the comparisons between tramadol HCl/diclofenac sodium 50 mg/50 mg and the monotherapies of diclofenac sodium 50 mg and tramadol HCl 50 mg, and using a non-inferiority margin of $\Delta = 1.5$ points (TOTPAR4) on the primary efficacy endpoint in the comparisons between tramadol HCl/diclofenac sodium 25 mg/25 mg and the monotherapies of diclofenac sodium 50 mg and tramadol HCl 50 mg. To achieve 180 evaluable subjects per arm and accounting that up to 10% of subjects will not be evaluable for the analysis set for the primary analysis, 200 subjects per arm or 800 subjects in total will be allocated to IMP.

Assuming an enrollment failure rate of about 25% which is usually observed in clinical trials in Mexico, about 1065 subjects are planned to be enrolled (i.e., sign the informed consent) in order to allocate 800 subjects to IMP, i.e., about 130 subjects per trial site in approximately 8 sites.

In summary, the study will be conducted at approximately 8 investigational sites in Mexico, and approximately 1065 patients will be enrolled.

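### The 180 per arm is not required for 85% power to reject at least 1 of 4 nulls: about 76 per arm suffices, and 180 fits a single non-inferiority test with an unstated zero difference

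*Protocol*

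**What the plan says.** Protocol 14.1.1 opens: "A total number of 720 subjects or 180 subjects per treatment group are required to achieve an overall power of at least 85"%. The number, together with the event being powered, is described as "required to achieve an overall power of at least 85% to reject the null hypothesis of at least 1 of the 4 formal statistical tests". The synopsis (1.6.1) and SAP 4 carry the same sentence.

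The inputs given there are:
- a test specification, "1-sided t-test, type I error of $\alpha/4$ with $\alpha = 2.5"%;
- a "common standard deviation of change from baseline values of 4 points (TOTPAR4");
- a difference of at least 2 points for 50/50 against each monotherapy;
- a non-inferiority margin of 1.5 points for 25/25 against each monotherapy.

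SAP 4 applies the margin "on the primary efficacy endpoint in the comparisons between tramadol HCl/diclofenac sodium 25 mg/25 mg and the monotherapies". Neither it nor the protocol gives an assumed true difference for those comparisons.

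The powered event is also the success rule. Protocol 14.5.2 states: "The trial will be positive if at least 1 of the according 4 statistical tests rejects the according null hypothesis". SAP 9.1 repeats this. The first Holm step tests the smallest p-value at 0.625%; if it passes, "reject $H_{(01)}$ and move to the next step. Otherwise retain all null hypotheses and stop". At least one rejection therefore means that at least one of the four p-values is below 0.625%.

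**The concern.** With a 2-point effect, an SD of 4 and 180 per arm, one superiority test is already very well powered at 0.625%. The chance that at least one of four tests succeeds must be higher still, so 85% looked far too low for the event named, or 180 far too high for the target.

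Two things are at stake. First, a reader who takes the sentence at face value will believe the trial has about an 85% chance of success under its own rule, and that 180 per arm is the price of it. Second, the sentence gives no power for any individual claim, and it omits the one assumption that drives non-inferiority power, the true 25/25 difference. The N cannot be reproduced without guessing that value.

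**Working it through.** **Inputs.** From protocol 14.1.1: SD σ = 4; per-test 1-sided level 0.025/4 = 0.00625; 50/50 minus each monotherapy = +2; margin Δ = 1.5. From protocol 1.4.1: 1:1:1:1 allocation. Not stated: the true difference d of 25/25 minus monotherapy. It is left free in step 2 and set to assumed values after that.

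**Step 1. Single tests at 0.625%.** For a two-sample t-test with n per arm, the noncentrality is θ / (σ√(2/n)), with 2n − 2 degrees of freedom. Here θ = 2 for superiority and θ = Δ + d for non-inferiority.

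At n = 180 the standard error is 4 × √(2/180) = 0.4216 and the critical value is 2.510.

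| Test | Noncentrality at n = 180 | Power at n = 180 | Smallest n for 85% |
|---|---|---|---|
| Superiority, difference 2 | 2/0.4216 = 4.743 | 98.7% | 102 (101 gives 84.8%) |
| Non-inferiority, d = 0 | 1.5/0.4216 = 3.558 | 85.2% | 180 (179 gives 84.95%, 180 gives 85.18%) |

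The second row reproduces the plan's 180 and 85% together. Other readings at 180 per arm with d = 0 do not give 85%: at least one non-inferiority test at 0.625% 94.4%, both about 76%, all four at 0.625% about 75%, all four under Holm about 90%.

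**Step 2. The event the plan names, with no assumption on 25/25.** T1 and T2 share the 50/50 arm, so their statistics have correlation 0.5. Power for at least one is 1 − P(both statistics fall below the critical value). With the normal approximation at n = 180, the critical value is 2.498, so each statistic must fall below 2.498 − 4.743 = −2.246 in standardised terms. The joint probability gives power 99.83%. With t critical values it is 99.8%.

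| n per arm | At least one of T1, T2 (t, pooled variance, 4n − 4 df) |
|---|---|
| 75 | 84.9% |
| 76 | 85.4% |
| 180 | 99.8% |

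The smallest n is 75 with the normal approximation, 76 with 4n − 4 df and 77 with 2n − 2 df. T3 and T4 can only add rejections, so about 76 per arm (4 × 76 = 304) is enough whatever d is. As a check, with d = −1.5 power for at least one of four is still 99.8% at 180 and 85.4% at 76. With d = 0 it is 99.9% at 180, and 85% is reached at 66 per arm (4 × 66 = 264).

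**Step 3. Power under the planned Holm procedure.** Simulated at 180 per arm, d = 0:

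| Event | Power |
|---|---|
| At least one of four | 99.9% |
| Each of T1, T2 / both | 99.5% / 99.0% |
| Each of T3, T4 / both | 93.3% / 89.8% |
| All four | 89.6% |

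**Step 4. Sensitivity to the unstated difference.** All d are assumed values, n = 180:

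| d | Single non-inferiority test at 0.625% | Each of T3, T4 under Holm |
|---|---|---|
| 0 | 85.2% | 93.3% |
| −0.25 | 67.5% | 81.2% |
| −0.5 | 44.6% | 60.3% |

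The value that matters is d on the analysed endpoint. Protocol 14.5.5 replaces post-rescue scores by 0.375 in the monotherapy arms and 0 in the combination arms, which is 0.375 × 2 h = 0.75 points for rescue at 2 hours. If, purely as an illustration, one third of each arm took rescue at 2 hours, the analysed difference would shift by 0.75/3 = 0.25 against 25/25.

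**Step 5. Dropout inflation.** 180/0.9 = 200 per arm, 800 in total. This agrees with the plan.

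**The case against.** The best defence is that nothing stated is numerically false. Power of 99.8% is at least 85%. The parenthesis describes one t-test at α/4, and sizing on the weakest of the four tests at the first Holm threshold is a legitimate sufficient condition: 85% for that test guarantees at least 85% for at least one rejection. On this reading 180 is a conservative N with poor wording, and the repair is documentary.

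Much of this stands. There is no power shortfall for the success rule, and 180 is a sensible N if each non-inferiority claim matters. But the text does not say that it sized on the weakest test; it says that 180 are required for at least one rejection, and they are not. The single-test reading also needs a zero 25/25 difference, which is nowhere stated.

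Two smaller points are fair. The bound of 76 moves between 75 and 77 with the choice of normal or t and degrees of freedom, against 180 stated. And a sensitivity line with only negative differences is one-sided. Protocol 18.3 reports that in the earlier bunionectomy trial one 25/25 tablet gave greater 4-hour total pain relief than diclofenac 50 mg. At d = +0.25 and +0.5 the single non-inferiority test has 94.9% and 98.7% power. That trial had no tramadol-alone arm, so it does not settle d for T3.

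**Conclusion.** The concern holds. With the plan's own inputs, 180 per arm gives at least 99.8% power for the event named, and 85% needs about 76 per arm at most, less than half the stated figure. This rests on the stated SD of 4, the 2-point difference in both superiority comparisons and the 0.625% level; it needs no assumption on 25/25.

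That a single non-inferiority test with zero difference set the N is an inference from an exact match, not something the documents say.

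The consequence is confined to the sample-size justification. No test, estimate or decision rule is affected. It should be fixed because the sentence misdescribes what the N delivers and leaves out the assumption on which non-inferiority power depends.

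**What to change.** In protocol 1.6.1 and 14.1.1 and in SAP 4, replace the power sentence with wording such as the following, once the sponsor has confirmed the 25/25 difference it assumed:

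> With 180 evaluable subjects per arm, SD 4 and 1-sided α/4 = 0.625%, power is about 85% for each single non-inferiority comparison (T3, T4) with margin 1.5 and an assumed true difference of zero on the analysed TOTPAR4, and about 98.7% for each superiority comparison (T1, T2) with an assumed difference of 2. Under the Holm procedure with the same assumptions, power is about 99.9% for at least one rejection; 99.5% for each and 99% for both of T1 and T2; 93% for each and 90% for both of T3 and T4; and 90% for all four.

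Add one line on sensitivity, labelled as assumed values: a single non-inferiority test at α/4 has 67.5% power at a true difference of −0.25 and 44.6% at −0.5. The sponsor may add +0.25 (94.9%) and +0.5 (98.7%) for balance.

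If the sponsor assumed a difference other than zero, that value should be stated and the figures that depend on it recomputed.

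The cost is wording in three sections. N, alpha, success rule, Holm procedure and analysis stay as they are, and no subjects are added.
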